### 7.2.2. Exclusion Criteria

A participant who meets any of the following criteria will be excluded from the study:

1. Has a life expectancy of less than 2 years
2. Weighs <40 kg (only applies to participants ≥12 to <18 years of age)
3. Has any signs or symptoms consistent with COVID-19 (as determined by the investigator)
4. Has a history of SARS-CoV-2 infection within 90 days prior to randomization
5. Planned use of any investigational, authorized, or approved vaccine for COVID-19 within 90 days (or per current CDC recommendations) of the last dose of study drug ([CDC, 2021](#))
6. Prior, current, or planned use of any of the following treatments: COVID-19 convalescent plasma, other monoclonal antibodies against SARS-CoV-2 (eg, bamlanivimab and

etesevimab, sotrovimab), or any COVID-19 treatment (authorized, approved, or investigational)

*Note: Prior use is defined as the past 30 days or within 5 half-lives of the investigational product (whichever is longer) from screening.*

7. Is planned to begin intravenous immunoglobulin (IVIG) or subcutaneous immunoglobulin (SCIG) therapy, is planned to have a change to existing IVIG or SCIG regimen, or has been on a chronic stable dose of their IVIG or SCIG regimen for less than 90 days prior to screening.
8. Has any known active acute respiratory infection
9. Has no documented laboratory blood chemistry and hematology (including differential) results in the 6 months prior to randomization
10. Has persistent (refractory to treatment for  $\geq 14$  days) bacterial or fungal infection
11. Has known allergy or hypersensitivity to components of the study drugs
12. Has been discharged, or is planned to be discharged, to a quarantine center
13. Is a member of the clinical site study team or their immediate family member

### **7.3. Premature Withdrawal from the Study**

A participant has the right to withdraw from the study at any time, for any reason, and without repercussion.

The investigator and/or Sponsor have the right to withdraw a participant from the study if it is no longer in the interest of the participant to continue in the study, or if the participant's continuation in the study places the scientific outcome of the study at risk (eg, if a participant does not or cannot follow study procedures). An excessive rate of withdrawals would render the study uninterpretable; therefore, unnecessary withdrawal of participants should be avoided.

Participants who are withdrawn prematurely from the study will be asked to complete the early termination visit, as described in Section [9.1.1](#).

Rules for permanent discontinuation of study treatment are discussed in Section [8.3.2](#).

### **7.4. Replacement of Participants**

Participants will not be replaced.

## 8. STUDY TREATMENTS

### 8.1. Investigational and Reference Treatments

Eligible participants will be randomized in a 1:1:1:1 allocation ratio to:

- Co-administered casirivimab+imdevimab combination therapy, 1200 mg (600 mg per mAb) on day 1, then 600 mg (300 mg per mAb) SC Q4W
- Co-administered casirivimab+imdevimab combination therapy, 300 mg (150 mg per mAb) SC Q4W
- Co-administered casirivimab+imdevimab combination therapy, 300 mg (150 mg per mAb) SC Q12W
- Placebo SC Q4W

In order to maintain blinding, additional placebo injections will be administered such that all participants receive the same number of injections and the same dosing frequency (Q4W).

For study drug administration which requires multiple SC injections, it is recommended to use different quadrants of the abdomen (avoiding navel and waist areas), front and upper outer sides of the thighs, or the back side of the upper outer area of the arm. During the dose administration, each injection must be given in a different anatomical location (eg, 1 injection administered in the right lower quadrant of the abdomen, another in the left lower quadrant of the abdomen, etc). Numbing cream at the sites of injection should not be used as this will interfere with the safety assessment, ie, evaluation of injection site reactions.

Instructions on dose preparation are provided in the pharmacy manual.

### 8.2. Background Treatment(s)

Participants may self-administer non-prescribed medications and continue other concomitant medications with the exception of those prohibited in Section 8.9.1. Participants will continue current treatments for their baseline conditions.

### 8.3. Dose Modification and Study Treatment Discontinuation Rules

#### 8.3.1. Dose Modification

Dose modification for an individual participant is not allowed.

#### 8.3.2. Study Drug Discontinuation

Participants who permanently discontinue from study drug should be encouraged to remain in the study. Participants who permanently discontinue from study drug and who opt to withdraw from the study will be asked to complete study assessments, per Section 9.1.1.

##### 8.3.2.1. Reasons for Permanent Discontinuation of Study Drug

Study drug dosing will be permanently stopped in the event of:

- Grade  $\geq 3$  injection-site reaction or grade  $\geq 3$  hypersensitivity reaction determined to be related to study drug

- Serious adverse event or other potentially life-threatening (grade 4) event that is determined to be related to study drug
- Investigator's clinical judgment, in coordination with principal investigator, that it is in the best interest of the participant
- Receipt of a COVID-19 vaccine during the study
- A positive baseline (day 1) result for SARS-CoV-2 from central laboratory RT-qPCR (however, eligible for additional treatment as defined in Section [6.4.7](#))
- Receipt of post-infection treatment with casirivimab+imdevimab (Section [6.4.4](#))
- Participant withdrawal of consent
- Unblinding of participant

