- Weekly central RT-qPCR test results and dates of sample collection
- Record of any post-infection treatment with casirivimab+imdevimab administered

Note that any sign or symptom considered by the investigator to be unrelated to baseline conditions and unrelated to treatments for baseline conditions will also be recorded and used for safety evaluation.

*Post-Infection Treatment.* Participants with confirmed positive SARS-CoV-2 RT-PCR will be eligible for post-infection treatment (as described in Section 6.4.4) at any time prior to receipt of the optional 1200 mg SC dose (eg, during the 4 weeks between receipt of the last protocol-defined dose and the optional 1200 mg SC dose). Once this optional dose has been administered, post-infection treatment will no longer be offered. Likewise, any participant who receives post-infection treatment will not be eligible to receive the optional 1200 mg SC dose.

*Participants with Positive SARS-CoV-2 RT-PCR.* Participants with a positive SARS-CoV-2 RT-PCR may have additional assessments and sample collections, during unscheduled visits every 7 days ( $\pm 1$  day) for central laboratory RT-qPCR analysis until 2 consecutive negative test results are obtained:

- NP swab samples for RT-qPCR
- COVID-19 signs and symptoms evaluated by the investigator or designee
- Information regarding COVID-19-related medically-attended visits (MAVs; defined in Section 9.2.4.3)

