#### **6.4.5. Schedule of Events for Participants with Positive SARS-CoV-2 RT-PCR**

Participants with a positive SARS-CoV-2 RT-PCR (from either local or central testing) will discontinue the study drug assigned at randomization and enter the follow-up period. This includes any participant for whom post-infection treatment with casirivimab+imdevimab was offered but was declined by the participant or investigator, or otherwise not received.

All participants with a positive SARS-CoV-2 RT-PCR will have **additional** assessments and sample collections, as noted in the Schedule of Events and summarized below):

- NP swab samples will be collected during unscheduled visits every 7 days ( $\pm 1$  day) for central laboratory RT-qPCR analysis until 2 consecutive negative test results are obtained. During these visits, COVID-19 signs and symptoms will also be evaluated by the investigator or designee.
- Information regarding COVID-19-related medically-attended visits (MAVs; defined in Section 9.2.4.3) will be recorded, and participants will be asked to notify study personnel as soon as possible about such occurrences.

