Note that any sign or symptom corresponding to a grade  $\geq 3$  TEAE will also be recorded and used for safety evaluation as described in Section [10.1](#).

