## 10. SAFETY EVALUATION AND REPORTING

### 10.1. Recording and Reporting Adverse Events

This study will collect and record the following targeted TEAEs:

- Treatment-emergent grade  $\geq 3$  AEs
- Treatment-emergent AEs leading to study drug discontinuation
- Treatment-emergent SAEs
- Treatment-emergent grade  $\geq 2$  hypersensitivity reactions
- Treatment-emergent grade  $\geq 3$  injection-site reactions

*Note: throughout Section 10, the term “AE” refers to the targeted list above.*

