#### 11.4.5. Safety Analysis

##### 11.4.5.1. Adverse Events

###### Definitions

For safety variables, the following observation periods are defined:

- The pretreatment period is defined as the time from the signing of the ICF to before study drug administration.
- The EAP is defined as the day from first dose of study drug to day  $169 \pm 7$  days
- The Follow-up period is defined as the end of the EAP to the end of the Follow-up Period (ie, the last study visit).

Treatment-emergent adverse events (TEAEs) are defined as those that are not present at baseline or represent the exacerbation of a pre-existing condition.

This study will collect data on the following targeted TEAEs (Section 10.1): Grade  $\geq 3$  AEs, AEs leading to discontinuation, SAEs, grade  $\geq 2$  hypersensitivity reactions, and grade  $\geq 3$  injection-site reactions.

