5.8. Analysis of Safety Data

Secondary safety endpoints are

1. Proportion of participants with grade ≥ 3 treatment-emergent adverse events (TEAEs), during the EAP and follow-up period
2. Proportion of participants with TEAEs leading to study drug discontinuation, during the EAP and follow-up period
3. Proportion of participants with treatment-emergent serious adverse events (SAEs) during the EAP and follow-up period
4. Proportion of participants with adverse events of special interest (AESIs) during the EAP

For safety variables, the following observation periods are defined:

- The pretreatment period is defined as the time from the signing of the ICF to before study drug administration.
- The EAP is defined as the day from first dose of study drug to day 169 ± 7 days
- The Follow-up period is defined as the end of the EAP to the end of the Follow-up Period (ie, the last study visit).

The safety analysis will be based on the reported AEs and other safety information (clinical laboratory evaluations, and vital signs). The summary of AE results will be presented for each treatment group for each of three TEAE periods: treatment-emergent EAP (TEEAP), treatment-emergent follow-up period (TEFUP), and overall study period (i.e., combined across the TEEAP and TEFUP). For laboratory and vital sign results they will be presented for each treatment group for each of three periods: EAP, follow-up, and overall study period.

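### Study drug stops that the protocol requires after a positive RT-PCR can be counted in the endpoint on TEAEs leading to study drug discontinuation, so that tolerability endpoint is contaminated by efficacy

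*Protocol*

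**What the plan says.** **The stop.** Protocol Section 6.4.5 says that participants with a positive RT-PCR, local or central, "will discontinue the study drug assigned at randomization and enter the follow-up period". This applies even if post-infection treatment is declined or not received. SAP 4.4.2 repeats the rule. Section 8.3.2.1, which lists the reasons for permanent discontinuation, is narrower. It names "Receipt of post-infection treatment with casirivimab+imdevimab" and a positive central result at baseline, but not a post-baseline positive test by itself.

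**The endpoint.** SAP 5.8 lists as its second secondary safety endpoint "Proportion of participants with TEAEs leading to study drug discontinuation, during the EAP and follow-up period". Protocol Section 4.2 has the same endpoint. Neither excludes COVID-19 events or stops that the protocol itself requires.

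**What is recorded.** Protocol Section 10.1 collects "Treatment-emergent AEs leading to study drug discontinuation" without a limit on grade or relatedness. Section 11.4.5.1 states: "Treatment-emergent adverse events (TEAEs) are defined as those that are not present at baseline or represent the exacerbation of a pre-existing condition". Section 10.1.1 makes an isolated diagnostic finding reportable as an AE if, among other conditions, it is symptomatic or leads to stopping study drug. Section 9.2.4.2 records COVID-19 symptoms as events of interest and sends to safety "any sign or symptom corresponding to a grade" 3 or higher TEAE. The site memorandum of October 2021 widened TEAE reporting beyond grade 3 and above. Amendment 2 adds: "any sign or symptom considered by the investigator to be unrelated to baseline conditions and unrelated to treatments for baseline conditions will also be recorded", with no grade threshold.

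**The concern.** The endpoint serves the secondary objective on safety and tolerability of repeated injections. A stop forced by a positive RT-PCR shows that the participant was infected, which is what the primary endpoint measures. It does not show that the injections were poorly tolerated.

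If the drug prevents infection and has no effect on tolerability, placebo will collect more of these stops and look worse tolerated. Real intolerance in an active arm could be offset by the same mechanism. This matters more after early closure. The Amendment 2 statistical summary commits to summarising all safety endpoints, while efficacy data only may be analysed, so safety is the main remaining output.

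**Working it through.** **1. Does a mandated stop enter the endpoint?** Three passages point towards counting it: AEs leading to discontinuation have no grade or relatedness limit (10.1), a diagnostic finding that is symptomatic or leads to discontinuation is an AE (10.1.1), and the TEAE definition excludes no endpoint events (11.4.5.1). One points away: 9.2.4.2 names only grade 3 or higher COVID-19 symptoms for safety, although the site memorandum and Amendment 2 later widened collection. No passage says whether a stop triggered by a test result is attributed to an AE. The endpoint can therefore include these stops, but the documents do not settle that it always does.

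**2. Reproduce Table 6.** Inputs from Section 11.2 and Table 6: placebo incidence 4.02% over 6 months; hazard ratios 0.40, 0.45 and 0.55 (from efficacy of 60%, 55% and 45%); 5% dropout; 10% outside the mITT set; 2188 per arm.
- Incidence = 1 − (1 − 0.0402)^HR = 1.628%, 1.829% and 2.231%, as stated.
- Cases = 2188 × 0.9 × l/(l+d) × (1 − exp(−(l+d))), where l = −ln(1 − 0.0402) × HR and d = −ln(0.95). This gives 31.25, 35.12, 42.84 and 77.18, total 186.4. The plan states 31, 35, 43 and 77, total 186.

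**3. Upper bound on the built-in gap.**
- Difference in incidence, arm 1 versus placebo: 4.02 − 1.628 = 2.39 points.
- The schedule has six Q4W doses, the last at about day 141, while cases count from day 2 to day 176. An infection after the last dose cannot stop a completed course. Days 142 to 176 are 35 of 175 days, which leaves 140/175 = 0.80.
- 2.39 × 0.80 = 1.91 points.
- With 5% dropout, applied to all 2188 per arm: 3.92% placebo and 1.59% arm 1. Times 0.80, these are 3.14% and 1.27%, a gap of 1.87 points.

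Both routes give about 1.9 points, if every illness is coded as a TEAE leading to discontinuation.

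**4. Effect on the comparison at planned size.** Assume equal true tolerability. The documents give no background rate b of other AE-related stops, so b = 0.5% to 5% is an assumption, as is the coded share f. Arm rate = b + f × (COVID-19 stop rate) × (1 − b).

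| f | b | Arm 1 | Placebo | Risk ratio |
|---|---|---|---|---|
| 100% | 0.5% | 1.76% | 3.62% | 0.49 |
| 100% | 2% | 3.24% | 5.08% | 0.64 |
| 100% | 5% | 6.21% | 7.98% | 0.78 |
| 10% | 2% | 2.12% | 2.31% | 0.92 |

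Without the mandated stops the ratio would be 1.0 in every row.

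**5. At the actual size.** With 66 enrolled, about 16.5 per arm, and a full 6 months at risk, expected infections are 16.5 × 0.0402 = 0.66 on placebo and 0.27, 0.30 and 0.37 in arms 1 to 3. The gaps are 0.39, 0.36 and 0.29 participant; times 0.80, about 0.3, 0.3 and 0.2. One event moves an arm by 1/17 = 5.9 to 1/16 = 6.3 points.

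**6. Would the SAP's output show it?** SAP 5.8.1 tabulates TEAEs leading to study withdrawal; TEAEs leading to study drug withdrawal get only a subject listing. Protocol 11.4.1 planned counts and reasons for stopping study treatment, but SAP 5.5 itemises only discontinuation of the study. The non-COVID TEAE overview in SAP 5.8.1 is explained in terms of underlying disease and covers study withdrawal. No specified summary separates mandated stops from intolerance by arm.

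**The case against.** The strongest objection is causal. The trigger is a test result, and Section 8.3.2.1 lists AE-based reasons apart from others such as vaccination, post-infection treatment and unblinding. A site could record a mandated stop with no AE as its cause. This stands in part: attribution is open, and sites could code the same event differently. Sections 10.1 and 10.1.1 still lean towards counting it.

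The Amendment 2 recording rule also applies once the Table 1 schedule has lapsed and only one optional dose remains, so little randomised dosing is left to discontinue. That is fair. The case rests on Sections 6.4.5, 10.1 and 10.1.1 and the site memorandum, which cover scheduled dosing.

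Other outputs give partial protection. Grade 2 or higher hypersensitivity and grade 3 or higher injection-site reactions have their own endpoint and summaries, so masking of those signals is unlikely. The protocol planned TEAEs leading to discontinuation by preferred term. With 66 participants, the SAP's listing can be read case by case.

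Finally, an all-causality count is a legitimate safety summary, and Section 3.3.2 commits the study to watching for antibody-dependent enhancement. That is a good reason to supplement the count and not replace it.

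**Conclusion.** The concern holds as contamination of unknown size and known direction. The endpoint can include stops caused by the primary efficacy event, and if the drug works this favours the active arms. The gap for arm 1 versus placebo is at most about 1.9 points at planning rates. This assumes exponential risk, a last dose at about day 141 and every illness coded this way; it shrinks in proportion to the coded share.

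Three stronger readings are tempting and are not supported:
- *That the endpoint simply measures efficacy, or that each COVID-19 illness counts.* Attribution is not settled, and other AE-related stops also enter.
- *That the gap equals the difference in infection incidence.* The 2.4-point difference includes infections after the last dose. The 4.6-point difference from the adult volunteer study in Section 3.3.1 (5.0% versus 0.4%) belongs to another population and regimen.
- *That Section 8.3.2.1 itself stops drug after any positive test.* For post-baseline positives, that rule is in Section 6.4.5 and SAP 4.4.2.

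For the 66 enrolled, the expected gap is under one participant per arm on planning rates, and all analyses are descriptive. Scheduled dosing cut short by closure, and reduced potency against Omicron, would make it smaller. A higher infection rate would make it larger: at five times the placebo hazard with HR 0.4, the full 6-month expectation is 1.3 in arm 1 versus 3.1 on placebo. The practical risk is that a single mandated stop shifts an arm by about 6 points and the summary tables do not show why.

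**What to change.** This is a reporting change only; no stopping rule is altered.

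- In SAP 5.8 and 5.8.1, keep the all-causality count of TEAEs leading to study drug discontinuation. Beside it, show the same count excluding stops mandated by a post-baseline positive RT-PCR or by post-infection treatment.
- Show those mandated stops on their own row, by arm.
- State in the SAP whether a mandated stop is attributed to a TEAE, so that coding is uniform.
- Tabulate TEAEs leading to study drug discontinuation by arm, in addition to those leading to study withdrawal.
- Reconcile Protocol Sections 6.4.5 and 8.3.2.1 on whether a positive RT-PCR alone is a listed reason for permanent discontinuation.

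The split concerns post-baseline positives. Baseline-positive participants (Section 6.4.7) are identified from a pre-dose sample, so treatment cannot affect their number.

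The cost is a short SAP clarification, one extra table row and a second version of the count. RT-PCR dates and dosing records are already collected.

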## **8.4. Management of Acute Reactions**

### **8.4.1. Acute Injection Reactions**

#### **8.4.1.1. Hypersensitivity Reaction (Systemic)**

Emergency equipment and medication for the treatment of systemic reactions must be available for immediate use. Hypersensitivities must be reported as AESIs if they meet the severity criteria defined in Section [10.1.3](#). The corresponding NCI-CTCAE severity scale is provided in Section [10.2.4](#).

Acute systemic reactions following SC injection of study drug should be treated using clinical judgment to determine the appropriate response according to typical clinical practice.

#### **8.4.1.2. Local Injection Site Reactions**

Local injection site reactions must be reported as AESIs if they meet the severity criteria defined in Section [10.1.3](#). The corresponding NCI-CTCAE severity scale is provided in Section [10.2.4](#).

## **8.5. Method of Treatment Assignment**

Participants will be randomized according to a central randomization scheme using an interactive web response system (IWRS).

Randomization will be stratified according to age categories (<18 years,  $\geq 18$  to  $\leq 65$  years,  $>65$  years), region (US, rest of world), and use of stable IVIG or SCIG regimen prior to screening (yes, no)

## **8.6. Blinding**

An unblinded pharmacist or qualified personnel at the site, not otherwise associated with the conduct of the study, will reconstitute the drug for administration. The drug solution must be provided in identical form for active and placebo treatments, so that they remain indistinguishable to both study personnel and participants.

Study participants, the principal investigators, and study site personnel (with the exception of the unblinded pharmacist at each site) will remain blinded to all randomization assignments throughout the study. The Regeneron medical/study director, study monitor, and any other Regeneron and contract research organization (CRO) personnel who are in regular contact with the study site will remain blinded to all participant randomization assignments.

Selected individuals from the Sponsor not involved in the conduct of the study may have access to unblinded data as needed for safety review or other data review. Any team performing interim data reviews will be separated from the ongoing study team. No study personnel involved in the day-to-day conduct of the study will have access to any unblinded data before the database is locked for this study.

Drug concentration, serology and other blood-based biomarker results will not be communicated to the sites, and the Sponsor's blinded operational team will not have access to results associated with participant identification until after the database is locked.

